### 5.2.1 Description of trial investigational products

#### 5.2.1.1 Placebo

---

Active substance	Lactobacillus acidophilus and Bifidoobacterium animalis
Trade or Generic name	Blackmores Acidophilus
Dosage form	Capsule
Route of administration	Oral one capsule daily for fifty days

---

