#### **3.1.2 Secondary objectives**

Secondary objective:

1. to determine if vitamin C prevents CRPS in patients with lower limb extremity trauma in a dose-response manner

2. to determine the incidence of CRPS in lower limb extremity trauma.
3. To determine the demographics and characteristics of patients who develop CRPS of the lower limb

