#### 4.4.2 Exclusion criteria

Patients meeting the following criteria will be excluded from the trial:

- Current or recent (ie less than three months prior to randomization) use of vitamin C, either as an isolated substance or as part of a multi-vitamin tablet. This is because the vitamin C dosing will not be standardized if patients are also taking the vitamin, and there is potential for overdosing. Vitamin C has a half-life of 10-20 days and therefore a long exclusion period is required.
- Patients who are pregnant or breastfeeding will be excluded due to the unknown safety risks in this patient population.
- Patients who are unable to commence taking the placebo/vitamin C medication within 72 hours after their surgery will be excluded from the trial
- Patients unable or unwilling to take oral medications.
- Patients who are vegan (as the placebo acidophilus is dairy based)

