### **5 INTERVENTION**

#### **5.1 Treatment arms**

There will be two treatment arms: placebo and vitamin C 500mg. Patients will be randomised to one of the two arms.

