#### 5.2.1.1 Vitamin C 500mg

---

Active substance	Ascorbic Acid (Vitamin C) 500mg Citrus bioflavonoids extract 50mg
Trade or Generic name	Amplio Vitamin C
Dosage form	Capsule
Route of administration	Oral one capsule daily for fifty days

---

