All hospital registrars and orthopaedic consultants will be given a verbal presentation to introduce the research project and the study investigators involved in the trial. This will be done at an orthopaedic weekly business meeting for approximately one hour. Education on trial design and CRPS examination and history will be provided. Study researchers will conduct follow-up history and examination.

Assessment at two weeks, six weeks, twelve weeks and twenty-six weeks is standard treatment for most bony and soft tissue injuries of the lower limb and does not deviate from normal procedure.

If a patient is diagnosed with CRPS, they will be referred to physiotherapy as per usual care. The method for which they are referred will depend on whether the patient is referred in the public or private systems:

- Public: a written referral will be made to the Physiotherapy Department at Peninsula Health. This is standard practice for a patient diagnosed with CRPS in this institution.
- Private: a written referral will be made to the patient's regular physiotherapist. If the patient does not have a regular physiotherapist, a choice of local, experienced physiotherapists will be offered for a referral and a written referral will be made. This is standard practice for management of CRPS in this system.

Patients will also be asked at each review appointment if they have adhered with the medication and if they are experiencing any side effects.

---

How has the patient felt since their last visit? (eg. fine, unwell, nauseated, in pain)

\_\_\_\_\_

---

Has the patient had any side effects to the medication such as abdominal upset, back pain, nausea or vomiting?

Yes  
 No

---

Has the patient taken the medication as prescribed?

Yes  
 No

If patients have skipped up to three consecutive dose of their medication, they will be

---

deemed 'non adherent and a note will be made on their Electronic Medical Record but will still be analysed to where they were randomised. If patients skip one dose they will be advised to simply continue the medication and not 'make up' a dose.

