### 11.3 Methods of analysis

The two secondary aims of this feasibility study will be addressed statistically. For the first secondary aim, diagnosis of CRPS will be ascertained in the form of time-to-event data, and rate ratios will be calculated using univariate Cox proportional hazards regression to directly compare diagnosis rates between the treatment and control groups.

Given the small sample size of this feasibility study, we anticipate randomization may inadequately balance the baseline characteristics of participants in the two treatment groups (e.g. age, trauma vs elective surgery). If necessary, a secondary set of analyses will be performed to adjust for baseline characteristics found to be imbalanced between groups to the extent of a 0.25 standard deviation difference in means (quantitative measures) or an odds ratio of 1.5 (binary measures). These analyses will be conducted using multivariate Cox proportional hazards regression models.

In the survival analyses, loss to follow-up will be considered a censoring event. This equates to an assumption that data is missing at random given the participant's treatment group and the timing of their loss to follow-up. The adequacy of this assumption will be checked in sensitivity analyses that will include both a multiple imputation by chained equations (MICE) approach and adjustment for baseline covariates predictive of propensity for dropout.

A sensitivity analysis will repeat the proportional hazards regression to compare rates of CRPS as diagnosed by the presence of individual Budapest criteria, rather than 3 out of 4 patient-reported symptoms or 2 out of 4 clinician-observed symptoms as required for formal CRPS diagnosis.

For the second secondary aim, the incidence risk of CRPS 6 months post surgery for lower limb extremity trauma patients will be reported as a proportion of the study sample.

Adverse events will be coded as per the Medical Dictionary for Regulatory Activities. Adverse events will be calculated at each visit, and patients may have more than one adverse event. Assessment of severity, frequency and relationship of adverse events to trial intervention will be presented by System Organ Class and information such as start date, stop date, severity, relationship expectedness, outcome and duration will be recorded. Adverse events leading to premature discontinuation from the trial intervention and serious treatment-emergent adverse events will be presented in a table.

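### The arms are labelled placebo and vitamin C 500mg, but the listed products differ in more than vitamin C, so an arm difference cannot be assigned to vitamin C alone

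*Protocol*

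**What the plan says.** Section 5.1 states: "There will be two treatment arms: placebo and vitamin C 500mg". The synopsis, section 4.1 (Overall design) and section 5.2.2 (Dosage) use the same two labels.

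The two tables headed 5.2.1.1 give the contents. For the placebo, the row for active substance reads "Lactobacillus acidophilus and Bifidoobacterium animalis", supplied as a marketed acidophilus capsule. For the other arm it reads "Ascorbic Acid (Vitamin C) 500mg Citrus bioflavonoids extract 50mg". The placebo's content appears once more, in section 4.4.2, as the reason for an exclusion: "Patients who are vegan (as the placebo acidophilus is dairy based".

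The first secondary objective (section 3.1.2) is "to determine if vitamin C prevents CRPS in patients with lower limb extremity trauma in a dose-response manner". Section 11.3 addresses it with a Cox model "to directly compare diagnosis rates between the treatment and control groups". At each review the clinician records an answer to "Has the patient had any side effects to the medication such as abdominal upset, back pain, nausea or vomiting" (section 7.4), and section 5.2.4 likewise has patients asked about gastrointestinal upset.

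**The concern.** The labels and the objective describe a comparison in which the arms differ by vitamin C. By the protocol's own tables, each arm receives listed active substances, and the vitamin C arm has a second one that the control lacks. A report that follows the objective would credit vitamin C with a difference, or with no difference, that belongs to a contrast between two products.

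Two readings are exposed. One is CRPS prevention, a secondary aim. The other is tolerability, which feeds the primary feasibility aim: section 3.2 judges suitability of the intervention by patient-reported compliance, complications and feedback. Section 5.2.3 treats gastrointestinal upset as a possible complication of vitamin C, so complaints in the two arms are likely to be read against each other. Section 2.1 foresees a larger trial. If that trial used a control of different content, tolerability differences seen here would not carry over without further assumptions.

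**Working it through.** There is no stated figure to reproduce: the point concerns what is compared, not sample size or power. The check sets the entries side by side and asks what the planned contrast identifies.

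1. **Contents by arm** (tables 5.2.1.1).

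| Component | Arm called vitamin C 500mg | Arm called placebo |
|---|---|---|
| Ascorbic acid | 500 mg | none listed |
| Citrus bioflavonoids extract | 50 mg | none listed |
| Bacterial product (two species) | none listed | yes |

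   Counting the bacterial product as one component, the arms differ in three, and the labels name one.

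2. **CRPS contrast** (section 11.3). Let C, B and P be the log hazard ratios for CRPS, each against an inactive capsule, of ascorbic acid, the bioflavonoids and the bacterial product. Taking C and B as additive:

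   observed log HR = (C + B) − P

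   This is one estimate for three unknowns. It equals C only if B = P, meaning both are zero or they cancel. An interaction between C and B would only add a further unknown.

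3. **Can the planned analyses separate them?** No. The covariate-adjusted Cox model, the imputation and dropout sensitivity analyses, and the analysis by individual Budapest criteria all keep the same two arms. Within the vitamin C arm, ascorbic acid and bioflavonoids come in one capsule at a fixed 500:50 ratio, so variation in adherence cannot separate them either.

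4. **Gastrointestinal complaints** (sections 5.2.4 and 7.4).

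   observed risk difference = risk on (ascorbic acid + bioflavonoids) − risk on bacterial product

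   This equals the effect of vitamin C against an inactive capsule only if the bioflavonoids add nothing and the bacterial product carries the same risk as an inactive capsule, or if departures from these two conditions cancel.

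5. **Is neutrality stated anywhere?** The risk sections (2.3.1 to 2.3.3) and the interaction list (5.2.7) discuss vitamin C. Section 4.4.2 mentions the acidophilus only because it is dairy based. No section says that the bacterial product or the bioflavonoids are expected to leave CRPS or side effects unchanged.

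6. **Mechanism only, on assumed values that are not in the protocol.** On the ratio scale, observed = vitamin C × bioflavonoids ÷ bacterial product. Suppose the true vitamin C ratio is 0.50 and each other component lies anywhere from 0.80 to 1.25:
   - lowest: 0.50 × 0.80 / 1.25 = 0.32
   - highest: 0.50 × 1.25 / 0.80 = 0.78
   - both at 1.00, or cancelling: 0.50

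   The departure can go either way. The range follows entirely from the assumed limits and does not estimate what happens in this trial.

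**The case against.** The strongest reply is that nothing is hidden and nothing false is claimed. The protocol never calls the control inert, it names the product and organisms, and it repeats the acidophilus content in the eligibility criteria. The short labels can be read as defined by the tables in the same chapter. CRPS prevention is secondary in a feasibility study of about 50 per arm. Section 11.3 plans to present adverse events by System Organ Class and specifies no between-arm test of gastrointestinal complaints. Recruitment, follow-up, data collection and resource outcomes do not depend on the control's content. The bioflavonoids are a 50 mg co-ingredient of a marketed capsule, and no passage suggests that this amount matters.

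Most of this stands, and it limits the point. A reader might infer that the control distorts the gastrointestinal comparison, that the bacteria are live, or that the comparison is biased. The documents support none of these: they name the organisms without saying they are viable, give no effect of either extra component on CRPS or on symptoms, and supply no rate from which a bias could be calculated. Nor do they support a charge of concealment.

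What the reply does not remove is the mismatch between the claim and the contrast. Disclosing the contents does not supply the neutrality assumption, and the objective and the analysis section still speak of vitamin C and of treatment against control. Composition, arm names and objectives are fixed in the protocol, so a separate analysis plan could not resolve this.

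**Conclusion.** The point holds as one of attribution. As written, the arm labels and the first secondary objective promise an effect of vitamin C, while the randomised comparison is vitamin C plus bioflavonoids against a bacterial product. The effect of vitamin C alone is not identifiable from it unless the other components are assumed neutral or cancelling, and the protocol makes and supports no such assumption.

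No size or direction can be given from the documents. The conclusion rests only on the two product tables being accurate. It touches the CRPS comparison and any between-arm reading of tolerability; the other feasibility outcomes are unaffected. It does not show that the trial's results would be wrong, nor that the products must be replaced.

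**What to change.** Reconcile the synopsis and sections 3.1.2, 3.2, 4.1, 5.1, 5.2.2 and 11.3 with the tables in 5.2.1.1:

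- Name each arm by its listed contents at first use: ascorbic acid 500 mg with citrus bioflavonoids extract 50 mg, and the *Lactobacillus*/*Bifidobacterium* comparator. Short labels may follow once defined.
- Reword the first secondary objective as a comparison of CRPS between these two products.
- Add a sentence to section 11.3 saying that CRPS and tolerability contrasts are between the two named products and are not attributable to vitamin C alone against an inactive control.
- If the sponsor wishes to keep an attribution to vitamin C, state the neutrality assumption for the other components openly and give its basis.
- Carry the same wording into the participant information and the report.

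The cost is a text amendment to the protocol and participant information, and a narrower claim. Dose, schedule, sample size and model are unchanged. Which products to use is for the sponsor.

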#### 5.2.1.1 Vitamin C 500mg

---

Active substance	Ascorbic Acid (Vitamin C) 500mg Citrus bioflavonoids extract 50mg
Trade or Generic name	Amplio Vitamin C
Dosage form	Capsule
Route of administration	Oral one capsule daily for fifty days

---

### 5.2.2 Dosage

Patients will be randomised to placebo or vitamin C 500mg. They will be blinded to their intervention arm until the end of the study.

Patients will take one capsule once per day, for fifty days. There is no restriction on the timing of the capsule and they can be taken with or without food.

### 5.2.3 Dose modification

In the very rare event that patients develop a complication from Vitamin C toxicity such as renal stones or gastrointestinal upset (this has never been documented in previous studies using this dose of vitamin C), they will be advised to cease taking the medication altogether. They will still be analysed using the intention to treat principle.

### 5.2.4 Storage, preparation, dispensing and administration of trial drug

The five sites will be allocated a box of medication from Peninsula Health pharmacy. This will be kept in a locked office with access only by the primary researcher at that site. Whilst on-site at Peninsula Health, this medication will be stored in pharmacy.

---

Patients will be educated on the dosage, timing and frequency of the medication and will be advised to take the capsules until the box is finished (50 days). Medication is self-administered.

In the setting of delayed or missed doses, patients will be told not to “make up” the dose but instead continue their normal daily dosing.

Patients will be asked at their review whether they have adhered to the medication schedule, if they had any problems with taking the medication or if any side effects such as gastrointestinal upset had occurred.

#### **5.2.5 Product accountability**

The trial medication will be sourced through pharmacy at Peninsula Health. The pharmacist will be responsible for randomising the medication and only the pharmacist will have access to the randomisation results. The patient and investigators will be blinded to the intervention. The pharmacist will maintain accurate records of the receipt of all trial medication including dates of receipt. Pharmacy will distribute the medication to the other three sites and these will be stored in a locked office.

Patients will be instructed to return leftover medication at the end of the fifty days (ideally there will be no leftover product as only fifty days’ supply will be provided) and reasons for departure from the expected dispensing regimen will be recorded. At the end of the trial, there will be final reconciliation of the trial drug received, dispensed, consumed and returned. Any discrepancies will be investigated, resolved and documented by the trial team. Unused trial drug will be destroyed in compliance with applicable regulations.

#### **5.2.6 Measurement of participant adherence**

Patients will be asked at their two-week, six-week, twelve-week and twenty-six week reviews whether they had been adherent with taking their medication. Adherence will be recorded in the medical record. If patients miss more than three doses at any stage in the preceding two weeks, they will be deemed non-adherent to the treatment protocol and participation withdrawn. Data up to that point will be analysed in the groups to which they were randomised following the intention-to-treat principle, but adherence will be noted and documented.

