### 5.2.9 Discontinuation from trial intervention

Participants who discontinue trial treatment will remain in the trial. The remaining trial procedures should be completed as indicated by the trial protocol.

Participants may discontinue trial treatment for the following reasons:

- Participant / legal guardian request to discontinue trial intervention
- Investigator decision to discontinue a participant from the trial intervention if the participant:
  - Is pregnant
  - Experiences a serious or intolerable adverse event such that continued trial intervention would not be in the best interest of the participant
  - Develops, during the course of the trial, symptoms or conditions listed in the exclusion criteria
  - Requires a medication that is prohibited by the protocol
  - Requires early discontinuation for any other reason

The investigator may also withdraw all trial participants from the trial treatment if the trial is terminated.

The procedure for transitioning a participant off the trial drug and/or onto alternate therapy is as follows: patients will be advised to cease taking the medication immediately and return the unused medication to the researcher.

For the safety of all participants ceasing trial treatment, the protocol-specified safety evaluations should be undertaken to capture new safety events and to assess existing, unresolved safety events. All scheduled follow-ups of trial participants should also occur following treatment discontinuation, where possible.

In addition to the safety evaluations, the data to be collected at the time of trial intervention discontinuation will include the following:

- Reason for discontinuing medication
- Any adverse effects
- Involvement of other practitioners in treatment of adverse events

A dedicated Case Report Form (CRF) page will capture the date and the specific underlying reason for discontinuation of the trial intervention.

The participant should remain in the trial for scheduled visits for trial assessments (follow-up) per protocol.

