### **11.2 Population to be analysed**

The study sample will be analysed via the intention-to-treat principle. Therefore, all randomised participants will be included analysis, regardless of whether they received and/or adhere to their allocated trial drug.

---

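### Section 5.2.6 ends follow-up for non-adherent participants, against the protocol's own stay-in-trial rule, and section 7.4 defines non-adherence differently

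*Protocol*

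**What the plan says.** Four places in the protocol deal with a participant who does not take the capsules.

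- **Section 5.2.6 (adherence).** The trigger is "If patients miss more than three doses at any stage in the preceding two weeks". The consequence is that "they will be deemed non-adherent to the treatment protocol and participation withdrawn". On analysis it adds: "Data up to that point will be analysed in the groups to which they were randomised following the intention-to-treat principle".
- **Section 7.4 (procedures).** The trigger is "If patients have skipped up to three consecutive dose of their medication, they will be" deemed non-adherent. The consequence is that "a note will be made on their Electronic Medical Record but will still be analysed to where they were randomised". Nothing is said about ending participation.
- **Sections 5.2.9 and 5.2.1 on discontinuation** (the second section numbered 5.2.1, listed as 7.5.1 in the contents). Both state: "Participants who discontinue trial treatment will remain in the trial". The second names significant non-adherence among the reasons for the investigator to stop treatment, under a heading that keeps the participant in follow-up, and it closes by requiring the scheduled visits to continue.
- **Section 11.2 (analysis population).** Here "all randomised participants will be included analysis, regardless of whether they received and/or adhere to their allocated trial drug".

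Adherence is asked about at the 2-, 6-, 12- and 26-week reviews. The form in sections 7.4 and 9.2.2 has one yes/no item on whether the medication was taken as prescribed. Section 5.2.5 adds a capsule return: "Patients will be instructed to return leftover medication at the end of the fifty days".

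**The concern.** The same participant can be withdrawn, followed to 26 weeks, or merely noted in the record, depending on which section a site follows. If sites follow section 5.2.6, outcome collection stops because of something that happened after randomisation.

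Missed doses may reflect side effects, pain or early symptoms. Section 11.3 treats loss to follow-up as censoring and assumes missingness at random given treatment group and timing. It does not mention withdrawal for non-adherence, and that assumption is hard to defend for a withdrawal triggered by the participant's own behaviour on treatment. The Cox comparison could be affected. So could the six-month incidence proportion: if withdrawn participants stay in the denominator, any later diagnosis counts as none.

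The primary objective is touched too. Follow-up at the set time points, the lost-to-follow-up rate and reported compliance are all primary feasibility outcomes in section 3.2. A rule that removes non-adherers makes part of the attrition itself. It also prevents the trial from learning whether such patients can be followed.

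**Working it through.** The protocol gives no adherence rate and no withdrawal rate, so there is no stated figure to reproduce. The finding rests on comparing the texts. The arithmetic only illustrates size.

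**1. The rules side by side**

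| Section | Trigger | Stays in follow-up? | Analysis |
|---|---|---|---|
| 5.2.6 | More than 3 missed in the preceding 2 weeks | No | As randomised, data to that point |
| 7.4 | Up to 3 consecutive skipped | Not addressed | As randomised |
| 5.2.1 (discontinuation) | Significant non-adherence, not quantified | Yes | Not addressed |
| 11.2 | Any level of adherence | Not addressed | All randomised |

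Rows 1 and 3 contradict each other directly on follow-up. Rows 1 and 2 do not identify the same people. One to three consecutive skips, with no other misses, meet section 7.4 but not section 5.2.6. Four scattered misses in two weeks meet section 5.2.6, while section 7.4 speaks only of consecutive doses.

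**2. What is lost at withdrawal**

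Follow-up is 26 × 7 = 182 days. For a participant not already diagnosed with CRPS:

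- Withdrawal at week 2 loses 182 − 14 = 168 days (168/182 = 92%), with the 6-, 12- and 26-week assessments.
- Withdrawal at week 6 loses 182 − 42 = 140 days (140/182 = 77%), with the 12- and 26-week assessments.

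The rule cannot act later. Treatment lasts 50 days, and the two-week look-back at week 12 starts at day 84 − 14 = 70.

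**3. How often it could be triggered (illustration)**

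Assumptions, none taken from the protocol: each daily dose is missed independently with probability p, and both on-treatment look-backs contain 14 dosing days.

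- One look-back: q = P(X ≥ 4) with X ~ Binomial(14, p), that is q = 1 − Σ C(14,k) pᵏ(1−p)¹⁴⁻ᵏ for k = 0 to 3.
- Either of two look-backs: 1 − (1 − q)².

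| Adherence (1 − p) | q | Either look-back | Of 100 participants |
|---|---|---|---|
| 95% | 0.0042 | 0.0083 | about 1 |
| 90% | 0.0441 | 0.0863 | about 9 |
| 85% | 0.1465 | 0.2716 | about 27 |
| 80% | 0.3018 | 0.5125 | about 51 |

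The first look-back may be shorter than 14 days. The synopsis puts the first review at 7 to 14 days after surgery, section 3.2 at 10 to 14 days, and dosing may start up to 72 hours after surgery. With 10 dosing days before the first review, P(X ≥ 4) is 0.0128 at 90% and 0.0500 at 85% adherence. The totals become:

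- 90%: 1 − (1 − 0.0128)(1 − 0.0441) = 0.056, about 6 of 100
- 85%: 1 − (1 − 0.0500)(1 − 0.1465) = 0.189, about 19 of 100

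With only 4 dosing days (7 − 3), all four must be missed. That has probability 0.10⁴ = 0.0001 at 90% adherence, so the first check almost never triggers.

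**The case against.** The best defence is that section 5.2.6 does not remove anyone from the analysis set. It analyses these people in their randomised groups, as section 11.2 requires. That stands. A reader might infer that the analysis is no longer by intention to treat, but the documents do not support this. What is missing is the follow-up after withdrawal, which section 11.2 needs in order to serve its purpose.

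Section 11.3 also plans multiple imputation and covariate-adjusted sensitivity analyses for loss to follow-up. They could be extended to these withdrawals, but they model outcomes that the protocol chose not to collect and do not replace them.

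On size, section 4.5 calls compliance in other trials excellent, which points towards the 95% row, about 1 in 100. That is a fair reading, and nothing in the protocol supports preferring the lower rows. Nor do the documents support a comparison between withdrawals and the expected number of CRPS events. They give no event rate for foot and ankle surgery, and the only lower-limb figure, 30% after tibial shaft fracture in section 2.2, would exceed the withdrawals in every row but the last.

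A reader might also conclude from the yes/no item that the dose rule cannot be applied at all. That goes too far. Clinicians ask about adherence and note it in the medical record, and section 5.2.5 records departures and reconciles returned drug. The narrower point holds: the form alone does not give a number of missed doses.

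Finally, the CRPS comparison is secondary and the sample size is not formally derived. This limits the inferential damage, but not the damage to retention as a primary feasibility outcome.

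**Conclusion.** The point holds as a contradiction in the text and needs no numerical assumption. Section 5.2.6 ends participation where the discontinuation section keeps the participant in follow-up, and section 7.4 defines the same condition by another threshold with another consequence. Followed as written, section 5.2.6 forgoes two or three of the four CRPS assessments on a post-randomisation criterion. Censoring may therefore be informative, but the documents allow neither the direction nor the size of any bias to be stated.

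The frequency is unknown. The illustration runs from about 1 to about 51 of 100 participants between 95% and 80% adherence, and lower when the first look-back is short. It depends entirely on the assumed adherence and on independent daily misses.

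This should be corrected before enrolment, because assessments not made cannot be recovered by any later analysis.

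**What to change.** 1. In section 5.2.6, delete the clause that ends participation and the words that limit the analysis to data before that point.
2. State there that non-adherent participants attend all outcome visits to 26 weeks and are analysed as randomised.
3. Reconcile sections 5.2.6, 7.4 and 5.2.1 (discontinuation) to one definition of non-adherence and one stated consequence for treatment. Whether non-adherence stops treatment is for the investigators to settle. This review does not propose a rule.
4. Record the number of missed doses at the on-treatment reviews and the date of the last capsule, in place of the yes/no item alone. Use the returned-capsule count only as support. Section 5.2.4 tells patients to continue until the box is finished and not to make up missed doses, so a participant may run past day 50, return nothing, and appear fully adherent on a capsule count.

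The cost is protocol wording and a few database fields (missed doses, date of last capsule, capsules returned). No visits are added to the schedule.
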